7.2. Secondary Endpoints

The secondary endpoints are:

- Additional viral load endpoints relating to antiviral effect include but are not limited to:
 - Peak viral load of RSV as defined by the maximum viral load determined by qRT-PCR measurements in nasal samples starting from initial administration of IMP up to planned discharge from quarantine (Day 12, am).
 - Time (days) to confirmed negative test by qRT-PCR measurements in nasal samples starting at initial administration of IMP to first confirmed undetectable assessment after peak measure.
 - Time (days) to confirmed negative test by qRT-PCR measurements in nasal samples starting from peak qRT-PCR after initial administration of IMP to first confirmed undetectable assessment after peak measure.
 - Time (days) to peak qRT-PCR in nasal samples, starting from initial administration of IMP.
 - Area under the viral load-time curve (VL-AUC) of RSV challenge virus as determined by viral culture on nasal samples, starting at initial administration of IMP up to planned discharge from quarantine (Day 12, am).
 - Peak viral load of RSV as defined by the maximum viral load determined by viral culture measurements in nasal samples starting from initial administration of IMP up to planned discharge from quarantine (Day 12, am).
 - Time (days) to confirmed negative test by viral culture measurements in nasal samples starting at initial administration of IMP to first confirmed undetectable assessment after peak measure.
 - Time (days) to confirmed negative test by viral culture measurements in nasal samples starting from peak viral culture after initial administration of IMP to first confirmed undetectable assessment after peak measure.
 - Time (days) to peak viral culture in nasal samples, starting from initial administration of IMP.
- Clinical symptom-related endpoints include, but are not limited to:
 - Area under the curve over time of total clinical symptoms (TSS-AUC) as measured from 10 symptoms within the graded symptom scoring system collected 3 times daily starting at initial administration of IMP up to planned discharge from quarantine (Day 12, am).
 - Area under the curve over time of total clinical symptoms change from baseline (TSS-AUCCFB) as measured from 10 symptoms within the graded symptom scoring system

collected 3 times daily starting at initial administration of IMP up to planned discharge from quarantine (Day 12, am).

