10.7.2. Secondary Endpoints

10.7.2.3 Viral Load Endpoints

Peak Viral Load of RSV as Defined by the Maximum Viral Load Determined by qRT-PCR Measurements in Nasal Samples Starting from Initial Administration of IMP up to Planned Discharge from Quarantine

Using the scheduled protocol assessments from the last measurement collected prior to the first dose of IMP to morning of Day 12 (Quarantine discharge), the highest qRT-PCR viral load value observed in nasal samples for each participant will be summarised and analysed in a similar fashion to the primary efficacy endpoint described in Section 10.7.1.

Participants who stay undetectable (i.e. a 'Not Detected' value) during quarantine will be replaced with the 'Not Detected' value shown in the table in Appendix 15.1.

Time to Confirmed Negative Test by qRT-PCR Measurements in Nasal Samples Starting from Initial Administration of IMP to First Confirmed Undetectable Assessment after Peak Measure

The time from the first administration of IMP to the first confirmed negative qRT-PCR test after the peak qRT-PCR measurement will be calculated in days as:

Date and time of first confirmed negative test after peak qRT-PCR measurement – Date of and time of first IMP administration.

A negative test is defined as two consecutive 'Not Detected' results in the qRT-PCR test, with the date and time of the first negative test being utilised in the calculations. The peak qRT-PCR is defined as the highest viral load value obtained by a participant after their first administration of IMP.

Participants who did not have a confirmed undetectable assessment after first administration of IMP are censored at their last detectable assessment after their peak qRT-PCR measurement. Participants who stay undetectable during quarantine will be excluded from this analysis. Participants who return a positive result after two consecutive 'not detected' results will remain within the analysis.

The time to confirmed negative test will be summarised descriptively by treatment group. Kaplan Meier [2] curves will be produced for each treatment group, overlayed on one plot. A supporting table will include the median, 25th and 75th percentiles for each group and will be accompanied by a log rank test to compare between RV299 and placebo with the corresponding p-value presented.

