[Kaplan-Meier plot: y-axis = cumulative proportion of participants without a negative test, x-axis = day relative to initial administration of IMP, one line for each treatment overlayed on the same plot].

Time to Confirmed Negative Test by qRT-PCR Measurements in Nasal Samples Starting from Peak qRT-PCR after Initial Administration of IMP to First Confirmed Undetectable Assessment after Peak Measure

The time from the peak qRT-PCR measurement after administration of IMP to the first confirmed negative qRT-PCR test will be calculated in days as:

Date and time of first confirmed negative test – Date and time of first IMP administration.

A negative test is defined as two consecutive 'Not Detected' results in the qRT-PCR test, with the date and time of the first negative test being utilised in the calculations. The peak qRT-PCR is defined as the highest viral load value obtained by a participant after their first administration of IMP.

Participants who did not have a confirmed undetectable assessment after their peak qRT-PCR after first administration of IMP are censored at their last detectable assessment. Participants who stay undetectable during quarantine will be excluded from this analysis.

The time to confirmed negative test will be summarised descriptively by treatment group. Kaplan Meier curves will be produced for each treatment group, overlayed on one plot. A supporting table will include the median, 25th and 75th percentiles for each group and will be accompanied by a log rank test to compare between RV299 and placebo with the corresponding p-value presented.

[Kaplan-Meier plot: y-axis = cumulative proportion of participants without a negative test, x-axis = day relative to initial administration of IMP, one line for each treatment overlayed on the same plot].

Time to Peak qRT-PCR in Nasal Samples Starting from Initial Administration of IMP

The time to the peak qRT-PCR measurement starting from the initial administration of IMP will be calculated in days as:

Date and time of peak qRT-PCR measurement – Date and time of first IMP administration.

The peak qRT-PCR measurement is defined as the highest viral load value obtained by a participant after their first administration of IMP. Participants who stay undetectable during quarantine will be excluded from this analysis.

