Date and time of first confirmed negative test after peak viral culture measurement – Date and time of first IMP administration.

A negative test is defined as a 'Not Detected' result in the viral culture test, with the date and time of the first negative test being utilised in the calculations. The peak viral culture measurement is defined as the highest viral load value obtained by a participant after their first administration of IMP. Participants who did not have a confirmed undetectable assessment after first administration of IMP are censored at their last detectable assessment after their peak viral culture measurement. Participants who stay undetectable during quarantine will be excluded from this analysis.

The time to the confirmed negative test will be summarised descriptively by treatment group. Kaplan Meier curves will be produced for each treatment group, overlayed on one plot. A supporting table will include the median, 25th and 75th percentiles for each group and will be accompanied by a log rank test to compare between RV299 and placebo with the corresponding p-value presented.

[Kaplan-Meier plot: y-axis = cumulative proportion of participants without a negative test, x-axis = day relative to initial administration of IMP, one line for each treatment overlayed on the same plot].

Time to Confirmed Negative Test by Viral Culture Measurements in Nasal Samples Starting from Peak Viral Culture after Initial Administration of IMP to First Confirmed Undetectable Assessment after Peak Measure

The time from the peak viral culture measurement after administration of IMP to the first confirmed negative viral culture measurement will be calculated in days as:

Date of and time first confirmed negative test – Date and time of first IMP administration.

A negative test is defined as two consecutive 'Not Detected' results in the viral culture test, with the date and time of the first negative test being utilised in the calculations. The peak viral culture measurement is defined as the highest viral load value obtained by a participant after their first administration of IMP. Participants who did not have a confirmed undetectable assessment after their peak viral culture measurement after first administration of IMP are censored at their last detectable assessment. Participants who stay undetectable during quarantine will be excluded from this analysis.

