Peak Daily Symptom Score: Individual Maximum Daily Sum of Symptom Score from Initial Administration of IMP up to Planned Discharge from Quarantine

The highest total symptom score recorded on each day, across the three assessments, for each participant will be summarised descriptively by treatment group and assessment day.

Time to Symptom Resolution as Measured from 10 Symptoms within the Graded Daily Symptom Scoring System Starting at Initial Administration of IMP to 24-hours Symptom Free

Symptom resolution is defined as a participant scoring 0 for the total symptom score for a 24 hour period (e.g a minimum of three consecutive symptom diary cards, each with a score of 0) after their peak symptom score.

The time from the assessment at the time of the first administration of IMP until symptom resolution will be calculated in days as:

Date and time of symptom resolution – Date and time of assessment at IMP administration.

The time to symptom resolution will be summarised by treatment group using descriptive summaries.

If the peak symptom score occurs on more than one day then the first occurrence will be selected. Participants who do not record 24 hours symptom free after their highest total symptom score during the quarantine period will be censored at their last assessment and participants who record no symptoms during quarantine will be excluded from this analysis.

Time to Symptom Resolution as Measured from 10 Symptoms within the Graded Daily Symptom Scoring System Starting at Peak Symptoms after Initial Administration of IMP to 24-hours Symptom Free

The time from the highest total symptom score following administration of IMP until symptom resolution will be calculated in days as:

Date and time of symptom resolution – Date and time of highest total symptom score.

The time to symptom resolution after the peak symptom score will be summarised by treatment group using descriptive summaries.

If the peak symptom score occurs on more than one day then the first occurrence will be selected. Participants who do not record 24 hours symptom free after their highest total symptom score during the quarantine period will be censored at their last assessment and participants who record no symptoms during quarantine will be excluded from this analysis.

Time to Peak as Measured from 10 Symptoms within the Graded Daily Symptom Scoring System Starting from Initial Administration of IMP to the Time of Peak Daily Symptom Score

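### Both secondary endpoints defined as time from viral peak to confirmed negative (qRT-PCR and culture) are calculated from first IMP dose, so neither is estimated as written

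*SAP*

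**What the plan says.** SAP 7.2 lists the qRT-PCR endpoint as "starting from peak qRT-PCR after initial administration of IMP to first confirmed undetectable assessment after peak measure", and protocol section 3 defines it the same way. Both documents define the culture endpoint in parallel.

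In SAP 10.7.2.3 the lead-in to the qRT-PCR derivation agrees with that definition: "The time from the peak qRT-PCR measurement after administration of IMP to the first confirmed negative qRT-PCR test will be calculated in days as". The formula that follows is "Date and time of first confirmed negative test – Date and time of first IMP administration". The culture endpoint has a from-peak heading and lead-in too, and its formula is "Date of and time first confirmed negative test – Date and time of first IMP administration".

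The preceding endpoint, which is meant to start at first dose, is calculated as "Date and time of first confirmed negative test after peak qRT-PCR measurement – Date of and time of first IMP administration".

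The Kaplan-Meier specifications for both from-peak endpoints put days since first dose on the x-axis. In SAP section 14, Tables 14.2.2.3.1 and 14.2.2.8.1 reuse the layout of Table 14.2.2.2.1. The only derivation note in that layout subtracts the date of first dose, uses dates without times, and adds 1.

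**The concern.** The label and the arithmetic disagree on where the clock starts. Time from first dose to negative combines two processes: how long the virus takes to peak after dosing, and how fast it clears afterwards. The from-peak endpoints exist to isolate the second. With first dose as the origin, that question goes unanswered for both assays. For qRT-PCR, one result would also appear under two titles, and a reader of the study report could take it as two findings on clearance.

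**Working it through.** **1. Error or convention?** Three places in the SAP point to an error.

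- The matching symptom endpoint in 10.7.2.4, time from peak symptoms to resolution, is calculated as "Date and time of symptom resolution – Date and time of highest total symptom score". There the peak is subtracted.
- Listing shells 16.2.6.1.2 and 16.2.6.2.2 have separate columns for time from dosing and time from peak, so two different quantities were intended.
- SAP section 11 declares six changes from the protocol, several of them to time-to-event endpoints. A change of origin is not among them.

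**2. Internal consistency.** For a participant with a confirmed negative, let N be the time from first dose to that negative and P the time from first dose to peak. SAP 10.7.2.3 defines time to peak qRT-PCR as peak minus first dose, which is P. The from-peak time must then be N − P. The written formula returns N, and the two agree only if P = 0. The excess for each participant is N − (N − P) = P.

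**3. The two qRT-PCR derivations side by side.**

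| Element | From first dose | From peak, as written |
|---|---|---|
| Origin in formula | first IMP | first IMP |
| Event | first of two consecutive Not Detected results, after the peak | first of two consecutive Not Detected results; after the peak according to the heading, but not stated in the formula |
| Peak | highest value after first dose | same |
| Censoring | last detectable assessment after the peak | last detectable assessment |
| Excluded | participants never detectable in quarantine | same |
| Test | log-rank | log-rank |

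Both derivations carry the rule "A negative test is defined as two consecutive 'Not Detected' results in the qRT-PCR test". In the first, participants without an event "are censored at their last detectable assessment after their peak qRT-PCR measurement". In the second the words about the peak are absent from the censoring point, but the peak is itself a detectable result, so the last detectable assessment cannot precede it and the censoring time is the same. With the event taken as after the peak, every event time and censoring time matches. The log-rank statistic and p-value are then identical by construction.

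The statement that participants who turn positive again stay in the analysis appears only under the from-dose endpoint. The from-peak text has no rule removing them, so this creates no difference.

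**4. Culture.** The origin is equally wrong, but the pair is not duplicated. The from-dose version accepts a single Not Detected result as negative, while the from-peak version requires two in a row.

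**5. Size.** The documents give neither N nor P. Under the assumption that P is 1.5 to 2 days and N is 5 to 6 days:

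- N − P runs from 5 − 2 = 3.0 to 6 − 1.5 = 4.5 days.
- The relative excess P/(N − P) runs from 1.5/4.5 = 33% to 2/3.0 = 67%.

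**6. Does the origin matter to the comparison?** An illustration used 30 infected participants per arm, within the 26 to 34 implied by 40 per arm and 65% to 85% infected (40 × 0.65 and 40 × 0.85). The viral curves were assumed, with treatment bringing the peak forward by 0.5 day and steepening decline 1.3-fold. Over 400 simulated trials, the from-dose log-rank test rejected at 0.05 in 93.0% and the correctly derived from-peak test in 86.8%. The verdict differed in 47 of 400, about 12%. Adding 1 to every time, as the shell note does, left the log-rank p-value unchanged. These figures show only that the two quantities are not interchangeable; they do not predict this trial.

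**The case against.** The strongest reply is that the intention is plain. Headings, lead-ins, the endpoint list and the listing columns all say *from peak*. A careful programmer might follow them, and two identical qRT-PCR columns would probably be noticed at output review. That supports calling this a drafting slip with one evident correction. It does not make the plan safe, because the formula is the operative instruction and the axis and the shared table note repeat it. Two programmers who both followed it would agree on the wrong values.

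A second reply also has force. The qRT-PCR from-peak formula leaves out the words placing the event after the peak. Read with complete literalness, an earlier pair of Not Detected results could count, and the two endpoints could then differ. The duplication therefore depends on the heading supplying the event. The wrong origin does not.

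Several stronger readings are tempting but not supported:

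- *The p-value is counted twice, inflating error.* SAP 10.1.7 makes no multiplicity adjustment, and no alpha or testing sequence depends on these endpoints. One result would be printed twice; no error-rate calculation changes.
- *The times are overstated by a fixed percentage, or by at least half a day.* No document gives time to peak. Washes and first dose each have a one-hour window either side, so the first post-dose wash can fall less than 12 hours after dosing.
- *The log-rank tests should be dropped.* SAP section 11 item 3 added them openly. Protocol Table 9-2 plans no inference for the culture from-peak endpoint and has no row for the qRT-PCR one. Whether to test is a separate choice from where the clock starts.

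**Conclusion.** The derivation is wrong as written for both from-peak endpoints and must be corrected. The error per participant equals the interval from first dose to peak; the 33% to 67% range above holds only under the stated assumptions. Repetition of the from-dose result applies to qRT-PCR alone, on the reading that the event follows the peak. The damage is confined to two secondary endpoints in a Phase 1b study. The primary AUC analysis, the analysis populations and the safety analyses are untouched.

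**What to change.** In SAP 10.7.2.3:

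- Change both formulas to the time of the first confirmed negative *after the peak* minus the time of the post-dose peak measurement.
- Relabel the two Kaplan-Meier x-axes as days from peak.
- State that the first occurrence is used when peak values tie, as 10.7.2.4 already does for symptoms.
- Reconcile the culture definitions of a negative test (one Not Detected result against two consecutive), or explain why they differ.

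In SAP section 14, give Tables 14.2.2.3 and 14.2.2.8 their own derivation note in date-and-time form, in place of the shared date-only note with its added 1.

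The log-rank tests may stay. The cost is a few lines of SAP text and shell notes, with no change to data collection or design. It should be done before unblinding, because moving the origin afterwards would be a post-hoc redefinition.

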10.1.4. Statistical Testing and Estimation

Statistical analyses for the primary and secondary endpoints will be performed using appropriate two-sided hypothesis tests at the 5% significance level.

For continuous data, an analysis of covariance (ANCOVA) will be used to compare means between the RV299 and placebo groups. The ANCOVA will have treatment group as a fixed effect and baseline viral load as a covariate, unless stated otherwise in the relevant endpoint section. Should data not satisfy the assumptions, an appropriate alternative test, e.g., Wilcoxon Rank-Sum test will be used.

P-values will be rounded to 4 decimal places. All p-values that round to 0.0000 will be presented as <0.0001 and p-values that round to 1.000 will be presented as >0.9999.

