10.7.1. Primary Endpoint

10.7.1.1 Main Analysis

The primary endpoint is the AUC of RSV-A Memphis 37b viral load measured in nasal washes by qRT-PCR, from the last measurement collected prior to the first administration of IMP until the last measurement collected up to the morning of Day 12 (Quarantine discharge). The viral load data will be supplied as \log_{10} copies/mL and will be used for this main analysis and to calculate the AUC using the trapezoidal rule [1].

The AUC will be summarised for RV299 and placebo using descriptive statistics and an ANCOVA with treatment group as a main effect and the baseline value as a covariate. The baseline value will be the qRT-PCR viral load value from the last measurement collected prior to the first administration of IMP. The treatment comparison will be presented, including the LS mean treatment difference with the corresponding two-sided 95% confidence interval and p-value. The equivalent Wilcoxon rank-sum tests will be provided in place of the ANCOVA where the assumptions of the parametric test are not met.

As nasal washes are scheduled to be taken twice daily for Days 2 to 11 (and once on Day 12), in order to calculate the AUC, the actual time that the assessment was collected will be used within the AUC calculation. The AUC calculation will be based on the available non-missing assessment values between the start and end of the defined AUC time period. However, for an AUC to be derived, a participant should have at least one non-missing data recording at the start of the AUC period (e.g. date of first administration of IMP) and also at the end of the AUC time period (e.g. Day 12). In addition, the participant should have at least 1 non-missing data recording on each day between the start and end of the defined AUC time period (i.e. at least 1 out of the 2 possible assessments on each Day)). Any missing data will be reviewed at the BDRM, for its potential impact on this endpoint, and any decisions to exclude participants as a result of these criteria will be documented in the BDRM minutes. For the reporting of AUC, where appropriate, qRT-PCR values that are 'Not Detected' or 'Detected' will be re-assigned using the substitution values shown in the table in Appendix 15.1.

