The time to peak qRT-PCR measurement will be summarised descriptively by treatment group. Kaplan Meier curves will be produced for each treatment group, overlayed on one plot. A supporting table will include the median, 25th and 75th percentiles for each group and will be accompanied by a log rank test to compare between RV299 and placebo with the corresponding p-value presented.

[Kaplan-Meier plot: y-axis = cumulative proportion of participants not yet reaching peak qRT-PCR, x-axis = day relative to initial administration of IMP, one line for each treatment overlayed on the same plot].

Area under the Viral Load-Time Curve (VL-AUC) of RSV Challenge Virus as Determined by Viral Culture in Nasal Samples, Starting from Initial Administration of IMP up to Planned Discharge from Quarantine

The area under the viral-load curve (VL-AUC) for RSV-A Memphis 37b measured in nasal washes by viral culture, from the last measurement collected prior to the first dose of IMP until the morning of Day 12 (Quarantine discharge) will be summarised and analysed as described in Section 10.7.1.

Viral culture analysis is only carried out on samples where the qRT-PCR results is at least detectable. Any missing viral culture results will be imputed with 'Not Detected' if the corresponding qRT-PCR result is not detected.

Peak Viral Load of RSV as Defined by the Maximum Viral Load determined by Viral Culture Measurements in Nasal Samples Starting from Initial Administration of IMP up to Planned Discharge From Quarantine

Using the scheduled protocol assessments from the last measurement collected prior to the first dose of IMP to the morning of Day 12 (Quarantine discharge), the highest viral culture measurement observed in nasal samples for each participant will be summarised and analysed in a similar fashion to the primary efficacy endpoint described in Section 10.7.1.

Participants who stay undetectable (i.e. a 'Not Detected' value) during quarantine will be replaced with the 'Not Detected' value shown in the table in Appendix 15.1.

Time to Confirmed Negative Test by Viral Culture Measurements in Nasal Samples Starting from Initial Administration of IMP to First Confirmed Undetectable Assessment after Peak Measure

The time from the first administration of IMP to the first confirmed negative viral culture measurement after the peak viral culture measurement will be calculated in days as:

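### Time to confirmed negative by viral culture uses a one-result rule when timed from first IMP and a two-result rule when timed from peak, so the two endpoints can date the same clearance differently

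*SAP*

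**What the plan says.** SAP section 7.2 gives both culture endpoints the same terminal event, the "first confirmed undetectable assessment after peak measure"; protocol section 3 words it the same way. SAP section 10.7.2.3 then defines the negative test separately for each endpoint:

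- Culture, from first IMP: "A negative test is defined as a 'Not Detected' result in the viral culture test".
- Culture, from peak: "A negative test is defined as two consecutive 'Not Detected' results in the viral culture test".
- qRT-PCR, from first IMP and again from peak: "A negative test is defined as two consecutive 'Not Detected' results in the qRT-PCR test".

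In all four cases the event is dated at the first negative result. The one-result paragraph still calls its event confirmed, and it censors participants who lack a confirmed undetectable assessment. Each of the four endpoints gets Kaplan-Meier curves and a log-rank p-value. SAP section 10.1.4 sets "appropriate two-sided hypothesis tests at the 5% significance level", and section 10.1.7 makes no multiplicity adjustment.

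**The concern.** One definition of four departs from the others, and it is the one that confirms nothing. SAP section 11 lists six changes from the protocol and this is not among them. The shared table shell for these endpoints does not define the word either, so a programmer has no other source from which to settle the rule.

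Two reported results are at stake. The culture tables can disagree about when the same participant cleared. The from-IMP times are also biased short for anyone whose culture is intermittently negative, because the first gap after the peak is taken as clearance. Longer shedders have more chances of such a gap. If placebo participants shed longer, their times are shortened more, and a true difference would tend to be attenuated.

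**Working it through.** The documents state no figure for this, so there is none to reproduce. The definitions are compared first, and an illustration follows.

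**1. A participant under both rules.** Take 12-hourly cultures after first IMP: detected at 12, 24 (peak) and 36 h; 'Not Detected' at 48 h; detected at 60 and 72 h; 'Not Detected' at 84 and 96 h.

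- From IMP, one-result rule: event at 48 h, 48/24 = 2.0 days.
- From peak, two-result rule: event at 84 h, (84 − 24)/24 = 2.5 days.
- Two-result rule for both: 84/24 = 3.5 days from IMP and 2.5 days from peak.

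Under the plan's rules the time from IMP is shorter than the time from a later origin, which is impossible if both measure the same event. The from-peak formula in the SAP actually reads "Date of and time first confirmed negative test – Date and time of first IMP administration", which subtracts the wrong start time. That is a separate error. Taken literally, it gives 3.5 days against 2.0 days for the same subtraction, so the contradiction remains.

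**2. The last wash.** SAP section 10.1.1 makes the Day 12 am assessment the last one used. A first 'Not Detected' there is an event under the one-result rule. Under the two-result rule it cannot be confirmed, so the participant is censored at the last detectable assessment.

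**3. Link to qRT-PCR.** Culture is run only on samples at least detectable by qRT-PCR. Under culture VL-AUC the SAP says: "Any missing viral culture results will be imputed with 'Not Detected' if the corresponding qRT-PCR result is not detected". If the same data feed this endpoint, one negative qRT-PCR result after the culture peak ends the culture endpoint, while the qRT-PCR endpoint itself needs two.

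**4. Illustration of size.** Assumptions, none of them from the documents: m = 6 post-peak washes that still hold virus, each missed independently with probability q, followed by true negatives.

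One-result rule: P(early) = 1 − (1 − q)^6.

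- q = 0.05: 1 − 0.7351 = 0.2649
- q = 0.10: 1 − 0.5314 = 0.4686
- q = 0.20: 1 − 0.2621 = 0.7379

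Two-result rule: let a(k) and b(k) be the probabilities that no two consecutive misses have occurred by wash k and that wash k was detected or missed, respectively. Start at a(0) = 1, b(0) = 0, with a(k) = [a(k−1) + b(k−1)](1 − q) and b(k) = a(k−1)q. Two misses within the six washes have probability 1 − a(6) − b(6). If a miss on the sixth wash, completed by the next true negative, also counts as early, b(6) is added and the total is 1 − a(6).

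| q | One result | Two results, both within the six | b(6) | Two results, last miss counted |
|---|---|---|---|---|
| 0.05 | 26.5% | 1.2% | 4.7% | 5.9% |
| 0.10 | 46.9% | 4.6% | 8.7% | 13.3% |
| 0.20 | 73.8% | 16.4% | 14.3% | 30.8% |

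With 12 hours between washes and the last miss counted, clearance is dated early by a mean over all participants of 0.48, 0.89 and 1.52 days under the one-result rule. Under the two-result rule the means are 0.05, 0.14 and 0.41 days. The size depends on m: at q = 0.05 the one-result mean runs from 0.24 days (m = 4) to 0.80 days (m = 8).

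**The case against.** The endpoint is one of several secondary time-to-event endpoints. Protocol Table 9-2 planned no inferential analysis for it; the log-rank test was added by the SAP. No confirmatory claim rests on it, and the primary qRT-PCR AUC, the analysis populations and the safety analyses are untouched. All of this stands, and it limits the severity.

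The intent is also partly recoverable. With three sibling definitions at two results and the word confirmed kept throughout, this looks like dropped wording rather than a deliberate choice. That is probably right, but the literal text is what would be programmed, and the correction is still needed.

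A reader might infer that one missed detection ends a participant's follow-up. It does not. Washes continue to Day 12 and every culture result is listed, so the rule only fixes the event date and either version can be recomputed.

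A reader might also infer that the rule could manufacture a treatment difference. The documents do not support that. With the same shedding pattern in both arms, the rule acts equally on both. A spurious advantage would need a specific pattern, such as RV299 prolonging low-level intermittent shedding, and nothing in the documents suggests one.

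**Conclusion.** Wrong as written, and should be fixed, but it is not a threat to the trial's main conclusion. The contradiction between the two culture endpoints follows from the text alone and needs no assumption about assay error. The downward bias in from-IMP times holds for participants with a post-peak gap in detection; attenuation of the treatment effect is conditional on placebo shedding longer.

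The percentages show the mechanism and should not be read as estimates of bias in this trial. They rest on an assumed miss rate, six low-level washes, independent misses and, for the higher two-result figures, counting a final miss followed by a true negative as early. Under either counting convention the one-result rule errs more often, by a factor of about 2.4 (73.8/30.8) at the least in the cases shown.

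**What to change.** Before unblinding, amend SAP section 10.7.2.3 as follows.

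- In the culture endpoint timed from first IMP, define a confirmed negative as two consecutive 'Not Detected' culture results after the peak, dated at the first of the two.
- State that a participant whose only negative is the unconfirmed Day 12 am wash is censored.
- State that setting culture to 'Not Detected' when qRT-PCR is not detected also applies to the culture time-to-negative endpoints. At present it appears only under culture VL-AUC, and section 10.1.5 allows no imputation unless an endpoint section provides for it, so this is a further explicit change.

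The cost is a few sentences and some additional censoring among participants whose first negative is the last wash. The documents give no basis for estimating how many that would be. If a one-result rule is really intended, the difference should instead be justified in section 11 and the event no longer called confirmed.
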